Background: The rapid establishment of gas exchange after birth is vital for survival and long-term health. When newborn infants fail to initiate spontaneous breathing, positive pressure ventilation (PPV) is the cornerstone of respiratory support immediately after birth. The aim of PPV is to inflate the lungs, create a functional residual capacity, deliver an adequate tidal volume (V_T), facilitate gas exchange, and stimulate breathing, without causing lung or brain injury. In the delivery room, PPV is routinely provided via a pressure-limited device (called a T-Piece resuscitator), where an arbitrary peak inflation pressure (PIP) is set, with the assumption an adequate and safe V_T will be delivered. An alternative approach would be using a ventilator to deliver volume-targeted ventilation (VT), whereby the PIP is adjusted to target a set V_T measured by an inline flow sensor. While several trials have evaluated the use of respiratory function monitors to adjust the delivered V_T during PPV, no trial has compared PPV with VT-PPV in the delivery room.

Methods: A randomized trial of VT-PPV vs. PPV during neonatal resuscitation in preterm infants at birth to assess feasibility of a definitive trial for the intervention. Preterm infants born between 23^{0/7} to 28^{6/7} weeks' gestation will be eligible. Patients will be randomized to either the intervention (VT-PPV) or the comparator (PPV) during respiratory support in the delivery room. The sample size will be 50 preterm infants. The primary outcome will be percentage of eligible participants (=infants requiring PPV) who have the intervention performed correctly without protocol deviation (=cross over to control group when randomized to VT-group). Secondary outcomes will include neonatal morbidities (e.g., death, severe brain injury, bronchopulmonary dysplasia; and severe retinopathy of prematurity).

Discussion: The VOLT-trial aims to assess feasibility of VT-PPV and will address gaps in the evidence regarding the optimal approach to the establishment of ventilation in the delivery room. We aim to use the results of this trial to inform the design of a large multi-centre trial.

Study Protocol Registration: <https://clinicaltrials.gov/study/NCT05144724>, identifier NCT05144724.

KEYWORDS

infant, extremely preterm, neonatal intensive care, delivery room, respiratory function tests, neonatal mortality

Introduction

Background and rationale

Limitations of current positive pressure ventilation practices in the delivery room

When newborn infants fail to initiate spontaneous breathing at birth, positive pressure ventilation (PPV) remains the cornerstone of respiratory support immediately (1–3). The purpose of PPV is to inflate and create functional residual capacity in the lung, deliver an adequate tidal volume (V_T), facilitate gas exchange, and stimulate breathing, all while minimizing lung and brain injury (4). Positive pressure ventilation (PPV) in the delivery room is usually provided via a face mask with a T-piece resuscitator, where peak inflation pressure (PIP) is selected without measuring the actual tidal volume (V_T) delivered. Instead, adequacy is judged by heart rate and chest wall movement, though studies show healthcare providers often cannot reliably assess chest wall movement (5–7).

Tidal volume variability and its link to lung and brain injury at birth

Preterm infants are susceptible to ventilation-induced lung injury, as the volume difference between functional residual capacity and total lung capacity is small in this population (8). Delivery room studies reported that V_T during mask PPV ranges between 0 and 31 mL/kg (6, 9–13). This is concerning as animal studies demonstrated that lung injury was predominantly caused by high V_T ventilation (>8 mL/kg) and if V_T was controlled to avoid lung over-distention, little or no injury occurred (14–22).

Similarly, studies in preterm lambs reported that PPV with $V_T > 8$ mL/kg causes brain injury through increased inflammation, hemodynamic instability, and oxidative stress (17–19). [name] et al. showed that preterm lambs ventilated with higher V_T (10–12 mL/kg) for the first 15 min after birth had highly variable cerebral oxygenation, as measured by near-infrared spectroscopy (NIRS), compared to preterm lambs ventilated with a protective strategy ($V_T < 8$ mL/kg) (19). Disruption of the blood-brain barrier was observed in 60% of preterm lambs ventilated with high V_T , as evidenced by vascular protein extravasation, but was not observed in preterm lambs ventilated with a protective strategy. These preclinical findings are supported by observational studies in the delivery room, which reported a four-fold increase in rates of severe intraventricular hemorrhage (IVH) in preterm infants (<29 weeks' gestation) when $V_T > 6$ mL/kg was delivered during PPV (23, 24). Therefore,

approached which could improve V_T delivery might reduce lung and brain injury.

Adjusting tidal volume to protect the preterm lung and brain

Randomized trials in the delivery room utilizing a Respiratory Function Monitor (RFM) during PPV, which allows the resuscitator to target V_T , has been associated with a lower rate of excessive (>8 mL/kg) V_T delivery (9–11). A systematic review of randomized trials comparing RFM visible vs. masked demonstrated confirmed that the proportion of infants receiving $V_T > 8$ mL/kg can be reduced with an RFM visible (25). However, rates of bronchopulmonary dysplasia were unchanged in all trials. Interestingly, brain injury (defined as any IVH and/or periventricular leukomalacia) can be reduced by 35% and any grade IVH by 32% with an RFM visible (25). Unfortunately, none of the randomized trials was powered to examine differences in brain injury (only reported as secondary outcomes), and therefore these results might have only occurred by chance.

Neonatologists are increasingly careful in the neonatal intensive care unit (NICU) to apply ventilation strategies that are gentle to the lungs (26, 27). Volume-targeted ventilation (VTV), where ventilators algorithmically adjust PIPs to target a set V_T as detected through an inline flow sensor, is routinely used in the NICU (26–28). A meta-analysis of VTV in the NICU showed a reduction in a number of adverse clinical endpoints, including (i) the incidence of pneumothorax (typical RR [95%CI] 0.46 [0.25–0.84], numbers needed to treat [95%CI] 17 [10–100]), (ii) hypoxemia (typical RR [95%CI] 0.56 [0.33–0.96], numbers needed to treat [95%CI] 4 [2–25]), (iii) combined outcome of death or bronchopulmonary dysplasia (typical RR [95%CI] 0.73 [0.57–0.93], numbers needed to treat [95%CI] 8 [5–33]), and (iv) the combined outcome of periventricular leukomalacia (PVL) or grade 3–4 IVH (typical RR [95%CI] 0.48 [0.28–0.84], numbers needed to treat [95%CI] 11 [7–50]) (27). However, despite the general acceptance of VTV in the NICU, clinicians appear less aware that the same gentle approach should be applied to PPV in the delivery room to reduce lung and brain injury immediately after birth [36, 43].

Unanswered question: does VTV improve outcomes compared to PPV in the delivery room?

Therefore, alternate methods of providing tight V_T control during PPV in the delivery room resuscitation of preterm infants is needed, given the complex interaction of mask leak, lung compliance, PIP, and resuscitator skill. Using VTV immediately after birth would provide continuity from the delivery room into the NICU. Tracy et al. compared mask PPV with a T-Piece or VTV during simulated neonatal resuscitation and reported a lower coefficient of variations and lower V_T delivery with ventilator driven VTV compared PPV with a T-Piece (29). Similarly, Jain et al. compared VTV via a mechanical ventilator to manual T-Piece PPV and reported improved volume targeting at different compliance settings and a reduction in mask leak during simulated mask ventilation

Abbreviations

WCHRI, women and children's health research institute; PPV, positive pressure ventilation; V_T , tidal volume; PIP, peak inflation pressure; VTV, volume-targeted ventilation; RFM, respiratory function monitor; HIE, hypoxic-ischemic encephalopathy; IVH, intraventricular hemorrhage; PVL, periventricular leukomalacia; NICU, neonatal intensive care unit; ROP, retinopathy of prematurity; SAE, severe adverse event; DSMB, data safety monitoring board; SURG-TLX, surgery task load index; VOLT, volume targeted mask ventilation versus pressure ventilation in preterm infants trial.

(30). These studies suggest that VTV is feasible at least during animal or simulated neonatal resuscitation. Furthermore, Menakaya et al. compared VTV with a PPV using a Flow-Inflating bag and reported that preterm infants can be safely and effectively resuscitated using a ventilator (31). However, no study has compared VTV with T-Piece resuscitator during neonatal resuscitation of preterm infants in the delivery room. Thus, a clinical trial using VTV in the delivery room is urgently needed to determine if (a) this method can be feasibly used in the delivery room and (b) can potentially improve outcomes by reducing bronchopulmonary dysplasia and brain injury in preterm infants.

Objectives

Primary objective

To determine feasibility and safety of a trial comparing VTV-PPV to PPV in extremely preterm infants.

Secondary objectives

To evaluate clinical outcomes and HCP experience of the VTV-PPV.

Primary research question

Population: In preterm infants born at 23⁰–28⁶ weeks' gestation is a trial of **Intervention:** mask ventilation using a mechanical ventilator (VTV-PPV) **Comparison:** compared to mask ventilation using a T-Piece Resuscitator (PPV) **Outcome:** feasible during mask ventilation in the delivery room, which will be assessed by percentage of eligible participants (=infants requiring PPV) randomized to the VTV group and receive the allocated intervention without protocol deviation (i.e., without crossover to the control group) **Timeline:** during the first 10 min after birth?

Secondary research questions

1. In preterm infants born at 23⁰–28⁶ weeks of gestation, does mask ventilation using a mechanical ventilator compared to mask ventilation using a T-Piece Resuscitator reduce neonatal morbidities (severe brain injury, bronchopulmonary dysplasia; and severe retinopathy of prematurity) and reduce the number of infants requiring intubation in the delivery room by transitioning more successfully to CPAP.
2. What qualitative feedback do HCPs have on the experience of using VTV-PPV in the delivery room?
3. How does VTV-PPV compared with PPV affect subjective workload reported by HCPs performing mask ventilation?

Trial design

A single centre randomized controlled trial.

Methods: participants, interventions, outcomes

Study setting

Royal Alexandra Hospital, Edmonton, Canada, a tertiary perinatal center admitting ~140 infants born between 23⁰ to 28⁶ weeks' gestation annually. The trial is registered on [clinicaltrials.gov](https://clinicaltrials.gov/study/NCT05144724) (<https://clinicaltrials.gov/study/NCT05144724>) (Table 1).

Eligibility criteria

Inclusion criteria (all must be satisfied)

- Born between 23⁰/⁷ to 28⁶/⁷ weeks' gestation based on best obstetrical estimates
- Considered suitable for full resuscitation, i.e., no parental request or antenatal decision to forego resuscitation
- Deferred parental consent post-intervention

Exclusion criteria

- Major congenital or chromosomal malformation
- Conditions that might have an adverse effect on breathing or ventilation (e.g., high risk for lung hypoplasia, congenital diaphragmatic hernia)
- Antenatally detected congenital heart disease requiring intervention in the neonatal period
- Antenatally diagnosed Hydrops requiring intervention in the neonatal period
- Neonatal resuscitation initiated before NICU team arrival
- Infants who are born outside of study center and transported to center after delivery

Consent or assent: who will take informed consent?

Informed parental/guardian consent will be obtained after the study intervention for ongoing data collection. The consent approach of obtaining individual consent after birth for data inclusion in the trial, will strengthen the number being recruited. Furthermore, this approach has been reviewed and approved by our local human ethics review board and is supported by the local Neonatal Family Advisory Care Team. For this important study to be feasible, and enroll a representative sample, an informed consent obtained after the study intervention for ongoing data is important, as obtaining consent prior to delivery can be difficult (32, 33). Guidelines for this approach as laid down by Tri-Council Policy Statement state that any study wishes to use deferred consent needs (34):

- a) “A serious threat to the prospective participant requires immediate intervention.” Infants participating in this trial will require respiratory support, which in most cases was unforeseen prior to delivery; hence these infants will all need PPV and using mask ventilation will be therapeutic. Although the pressure limited PPV method (PPV group) is the routinely used method at the participating site, it would

TABLE 1 Trial timeline.

Time point	Enrolment	Allocation	Post-allocation	Hospital discharge
	Antenatal	At birth	7–10 days of age	
Enrolment				
Eligibility screen	X	X		
Informed consent			X	X
Maternal demographic and pregnancy data			X	
Randomization data		X		
Baseline infant data			X	X
Interventions				
Intervention		X		
Outcome assessments				
Safety Assessment In-hospital Mortality (Part of primary outcome)		X	X	X
Safety Assessment Intraventricular hemorrhage			X	
Completion of admission data				X
Primary Outcome: Feasibility to recruit 50 preterm infants requiring PPV over a 2-year period				X

not be feasible for a neonatal resuscitation study to ask permission prior to delivery from every parent delivering within the participating site.

- b) “either no standard efficacious care exists or the research offers a realistic possibility of direct benefit to the participant in comparison with standard care.” The currently used approach in the delivery room is pressure limited PPV. However, in the NICU, VTV is standard of care for providing mechanical ventilation, not for resuscitation on NICU. The available animal evidence and limited neonatal data suggest that the interventional approach has the potential to improve standards of care.
- c) “either the risk is not greater than that involved in standard efficacious care, or it is clearly justified by the prospect for direct benefits to the participant.” Resuscitation is therapeutic and the currently available evidence suggest that the interventional approach (*VTV-PPV group*) has no higher risk of harm compared to the current standard of care (*PPV group*). Furthermore, the intervention approach is routine standard practice in the NICU, and has been shown to decrease combined outcomes of death/bronchopulmonary dysplasia and brain injury.
- d) “the prospective participant is unconscious or lacks capacity to understand the risks, methods and purposes of the research project.” A person in labor cannot give a valid informed consent to a research study. Thus, the parents will be informed as soon as possible after stabilization of the infant about the study and asked to consent to the use of data that have been collected on their child.
- e) “third party authorization cannot be secured in sufficient time, despite diligent and documented efforts to do so;” The parents will be informed as soon as possible after birth about the study and asked to consent to the use of data that have been collected on their child.
- f) “No relevant prior directive by the participant is known to exist.”
- g) There is an increasing use of the deferred consent approach within delivery room research. The steering committee of

this application has ample experience with using this approach during neonatal resuscitation studies.

[figure not shown]
Consent or assent: ancillary studies

Parents of participating infants will be asked if they agree to use of their data should they choose to withdraw from the trial. Participants will also be asked for permission for the research team to share relevant data with people from the Universities taking part in the research where relevant. This trial does not involve collecting biological specimens for storage.

Interventions

Choice of comparators

In the delivery room, PPV is routinely provided via a T-Piece resuscitator, where a PIP is arbitrarily chosen, with the assumption it will deliver an adequate V_T . However, the delivered V_T is not measured and therefore PIP is not adjusted to optimize V_T delivery. While a lung-protective strategy must start immediately after birth, this has not been studied in detail. Lung compliance and the corresponding PIP needed to deliver an appropriate V_T vary between infants depending on gestational age, disease state and delivery mode (C-section vs. vaginal). In addition, the optimal PIP and V_T for an individual infant change in the first minutes after birth as lung fluid is cleared and the lung aerated. Therefore, relying on a fixed PIP and subjective assessment of chest rise may result in harm by either under- or over-ventilation. It may be beneficial to measure and adjust the V_T delivered during PPV in the minutes after birth, especially in very preterm infants at the greatest risk of lung and brain injury. Delivery room studies reported that V_T during PPV ranges between 0 and 31 mL/kg, which is concerning as animal studies reported that lung injury was predominantly caused by high V_T ventilation (>8 mL/kg). This led to the utilization of RFMs during

PPV to target V_T . Three trials compared an RFM visible to adjust the delivered V_T to RFM masked, which resulted in a reduction of $V_T > 8 \text{ mL/kg}$ being delivered, but failed to reduce rates of bronchopulmonary dysplasia. Therefore, alternate methods of providing tight V_T control during PPV in the delivery room resuscitation of preterm infants is needed. In the NICU, VTV ventilators which algorithmically adjust PIPs to target a set V_T are routinely used. A meta-analysis of trials comparing VTV with pressure guided ventilation in the NICU showed a reduction in pneumothorax, combined outcome of death or bronchopulmonary dysplasia, combined outcome of PVL or grade 3–4 IVH. However, despite the general acceptance of VTV in the NICU, this approach is not used in the delivery room to reduce lung and brain injury immediately after birth. The trials will compare VTV-PPV with PPV during respiratory support immediately after birth to assess the feasibility of VTV-PPV.

Intervention description

Treatment arms

PPV group

The clinical team will proceed through all steps of the neonatal resuscitation algorithm, as per current neonatal resuscitation

guideline (1–3) and local hospital policy (standard hospital practice guideline). Mask ventilation in the delivery room will be provided as per local hospital policy (standard hospital practice guideline). At the Royal Alexandra Hospital, mask ventilation is delivered with a T-piece device with initial settings of PIP of 24 cmH₂O, a peak expiratory pressure PEEP of 6 cmH₂O, a max PIP of 40 cmH₂O and a gas flow rate of 8–10 L/min. Resuscitators are trained to use a ventilation rate of 40–60 inflations/min. The clinical team will determine if/when ventilation pressures (both PEEP and PIP) should be increased, as per local hospital policy (standard hospital practice guideline), using clinical assessments (heart rate, oxygen saturation, auscultation, chest raise) (Figure 1).

VT-PPV group

Initial ventilation settings for VTV-PPV will be a VT of 5 mL/kg, a ventilation rate of 50 inflations/min, a maximum PIP of 40 cmH₂O, and a PEEP of 6 cmH₂O. For VTV-PPV, a size 9.0 endotracheal tube connector will be inserted into the facemask to allow secure attachment of the flow sensor and ventilator circuit. Ventilation will be delivered using PC-CMV with Volume Guarantee, beginning at 5 mL/kg and adjustable up to 6 mL/kg if required. The trigger sensitivity will be set at 0.2 L/min to enable infant-triggered breaths, and the inspiratory time

will be set at 0.3 s, with the option to increase to 0.5 s based on clinical response. To minimize leak, clinicians will use a two-hand mask-hold technique, as the ventilator tubing is heavier than a T-piece and may otherwise create downward pull. The clinical team will proceed through all steps of the neonatal resuscitation algorithm, as per current neonatal resuscitation guidelines (1–3) and local hospital policy but will replace standard pressure-limited PPV with VTV-PPV in the intervention group. The clinical team will determine if and when V_T , ventilation rate, and/or PEEP should be increased, using clinical assessments (heart rate, oxygen saturation, auscultation, chest rise). In addition, the clinical team will be trained to troubleshoot ventilator alarms such as low minute ventilation (e.g., airway obstruction) and disconnect alarms (e.g., mask leak) (Figure 1). No CO_2 monitoring (end-tidal or transcutaneous) will be used due to feasibility limitations in the delivery room.

Duration of treatment period

The study intervention will be applied for the first 10 min after birth.

Criteria for discontinuing or modifying allocated interventions

In any cases where the resuscitation team believes, that VTV-PPV is not working, the resuscitation team can revert to standard hospital practice guideline of administering PPV using a T-Piece resuscitator at any time.

If HR <60 at any time despite 30 s of effective ventilation, the resuscitation guidelines state to use an alternate airway and start chest compression. At that time, the VTV-PPV approach must be abandoned and a T-Piece must be used.

Strategies to improve adherence to interventions

Training logs and continuing engagement during daily clinical huddles to remind about the study.

Relevant concomitant care permitted or prohibited during the trial

Other than providing PPV with either a ventilator (intervention) or a T-Piece (standard of care), all delivery room interventions will follow the center's local hospital policy (standard hospital practice guideline) and the current neonatal resuscitation guidelines (1–3).

Provisions for post-trial care

Care during the primary hospitalization will adhere to local practice guidelines.

Outcomes

Primary outcome

Percentage of eligible participants (=infants requiring PPV) who have the intervention performed correctly without protocol deviation (=cross over to control group when randomized to VTV-group).

Secondary outcomes

Secondary outcomes include:

1. All-cause in-hospital mortality
2. Severe brain injury on cranial ultrasound: Severe grade 3 and 4 intraventricular or intraparenchymal hemorrhage according to Papile (35), periventricular leukomalacia, or ventriculomegaly based on neuroimaging studies (timing and frequency of imaging based on local site practices)
3. Severe retinopathy of prematurity (stage 3 or higher) as defined in the International Classification of ROP, and/or ROP treated with laser, cryotherapy, or intraocular injection therapy (36)
4. Bronchopulmonary dysplasia at 36 weeks corrected age and at 40 weeks corrected age, defined as receiving any supplemental oxygen or any form of respiratory support (including invasive mechanical ventilation, non-invasive ventilation with continuous positive airway pressure, nasal intermittent positive pressure ventilation, or high-flow nasal canula)
5. Total duration of mechanical ventilation via an endotracheal tube in days
6. Discharge home on oxygen
7. Duration of any respiratory support (invasive mechanical ventilation, non-invasive ventilation with continuous positive airway pressure, nasal intermittent positive pressure ventilation, or non-invasive neural assist ventilation or non-invasive high frequency ventilation, or high-flow nasal cannula) in days
8. Duration of supplemental oxygen in days
9. Length of hospital stay in days
10. Rate of intubation in the delivery room
11. Rate of chest compression in the delivery room
12. Rate of pneumothorax (diagnosed by chest x-ray or lung ultrasound) and interventions (e.g., needle drainage or chest drain)
13. Necrotizing enterocolitis, Modified Bell's criteria stage 2 or greater (37)
14. Duration of positive pressure ventilation at birth (within the first 10 min)
15. Resuscitators subjective workload performing mask ventilation, as evaluated by Surgery Task Load Index (SURG-TLX)-questionnaire.

16. Resuscitators qualitative feedback on using VTV-PPV in the delivery room, provided through free text responses.

neonatal deliveries will open an envelope with the group assignment and will enroll participants.

Participant timeline

Sample size

This will be a trial to assess the feasibility of VTV-PPV in the delivery room. Our primary outcome will assess the percentage of eligible participants (=infants requiring PPV) who have the intervention performed correctly without protocol deviation (=cross over to control group when randomized to VTV-group). We aim to recruit a sample of 50 infants (25 per arm) randomized 1:1 to VTV-PPV or PPV. The proposed sample size should be reached within 24 months. This study will be an initial trial for a large multi-center trial.

Recruitment

The study will be carried out at the Royal Alexandra Hospital, Edmonton, Canada, a tertiary perinatal center with ~6,000 deliveries annually admitting ~140 infants born between 23^{+0} to 28^{+6} weeks' gestation annually. Approximately 60% of babies born between 23 and 28 weeks' gestation require PPV at birth. The study site has a long history of conducting randomized trials and has the proven capability of enrolling the required number of infants. The number of infants being recruited will be 50, as per sample size. The overall recruitment period is a maximum of 24 months. There will be 50 infants recruited in Canada.

Assignment of interventions

Allocation

Sequence generation

The Biostatistics Unit at Women and Children's Health Research Institute (WCHRI), University of Alberta, Edmonton, Canada, will prepare the randomization schedule. Before trial initiation, a statistician will generate the 1:1 allocation sequence with computer-generated random numbers, which a second statistician will independently validate.

Concealment mechanism

The site's allocation sequence is password-protected, with access restricted to the independent statistician.

Implementation

Before the start of the trial, the statistician will use computer-generated random numbers to prepare the allocation sequence by producing the codes and allocation table. Clinical staff attending

Assignment of interventions: blinding

Who will be blinded

Blinding will not be feasible in the delivery room, as the healthcare providers will use two different ventilation devices including the VN 500 Ventilator (VTV-PPV Group) and the Neopuff T-Piece (PPV Group). The outcome assessor will be unaware of the group allocation. This blinding will be maintained until the data is locked for the final analysis, which will be performed blinded to group analysis and then un-blinded.

Procedure for unblinding if needed

Members of the Data Safety Monitoring Board (DSMB) will access unblinded treatment allocations to determine causality for any severe adverse events (SAEs) or other serious trial-related events.

Data collection and management

Plans for assessment and collection of outcomes

The VOLT investigators and research nurses will collect data from maternal and infant paper or electronic medical records. Data will be entered into a REDCap™ (Vanderbilt University) electronic database, designed and managed at the University of Alberta. REDCap is a secure, web-based application that supports data capture for research studies, including database management, survey design, and audit trails to ensure data integrity.

Plans to promote participant retention and complete follow-up

We are anticipating a <5% loss to follow-up until hospital discharge. The center has conducted more than 20 neonatal trials in the delivery room with lost-to-follow-up rates for the primary outcome of <5%.

Data management

VOLT investigators and research nurses will collect maternal and infant data from paper or electronic records and enter it into REDCap™ (Vanderbilt University), a secure, web-based research database designed and managed by the University of Alberta (38, 39).

Confidentiality

Participant data will be handled in compliance with applicable data protection and privacy regulations. All data will be securely stored, with electronic records accessible only to authorized research team members via password protection. Data will be de-identified, and participant anonymity will be maintained in all scientific publications and presentations.

Biological specimens

There will be no biological specimens collected.

Statistical methods

Statistical methods for primary and secondary outcomes

WCHRI will handle, verify, and analyze VOLT-trial data, with statistical methods aligned to standard randomized trial practices. Results will be reported in compliance with CONSORT guidelines.

The primary analysis will be conducted using an “intention-to-treat” approach. The primary analysis will focus on feasibility defined as percentage (75% or greater) of eligible participants (=infants requiring PPV) who have the intervention performed correctly without protocol deviation (=cross over to control group when randomized to VTV-group). Analysis of secondary outcomes will include the above-mentioned secondary outcomes using descriptive statistics. Summary statistics will be presented for baseline and clinical characteristics; continuous data by mean, two-sided 95%CI of the mean, standard deviation, median, interquartile range (first and third quartiles), minimum and maximum. Categorical data will be presented by absolute and relative frequencies. The clinical characteristics and outcome parameters will be compared using Student’s *t*-test for parametric and Mann-Whitney *U*-test for nonparametric comparisons of continuous variables, and χ^2 for categorical variables. The analysis will be 2-sided and *p*-value <0.05 will be considered statistically significant.

Interim safety analyses

The DSMB will conduct one interim safety analyses throughout the trial to assess in-hospital mortality and SAEs after 24 (50%) infants recruited.

Methods for additional analyses (e.g., subgroup analyses)

At the end of each intervention, the clinician’s workload will be assessed using the Surgery Task Load Index (SURG-TLX)-questionnaire (40). The SURG-TLX- questionnaire is a multidimensional workload measure to assess the impact of six various sources of stress on the perceived demands of trained healthcare professionals. These six aspects are then combined into a total workload score.

The SURG-TLX- questionnaire will assess:

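### BPD and the day counts can be pre-empted or cut short by death, but no listed secondary outcome combines them with death (minor and cheap to improve)

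*Protocol*

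**What the plan says.** Protocol, Secondary outcomes, gives 16 items. Mortality stands alone as the first: "All-cause in-hospital mortality". The fourth is "Bronchopulmonary dysplasia at 36 weeks corrected age and at 40 weeks corrected age, defined as receiving any supplemental oxygen" or any form of respiratory support. Four others are counts of days: "Total duration of mechanical ventilation via an endotracheal tube in days", "Duration of any respiratory support", "Duration of supplemental oxygen in days" and "Length of hospital stay in days". None of these carries a denominator or a rule for infants who die first, and no item is a composite with death. The abstract names death beside the morbidities as examples, not as a combined endpoint.

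Protocol, Statistical methods for primary and secondary outcomes, first calls the secondary analysis descriptive. It then says "The clinical characteristics and outcome parameters will be compared using" a t-test or Mann-Whitney test for continuous variables and chi-square for categorical ones, two-sided at 0.05. Intention-to-treat is stated for the primary analysis only. The missing-data sentence under Analysis population and missing data does not mention death.

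The combined outcome of death or BPD does appear elsewhere. It is cited as evidence for volume targeting in the background (Adjusting tidal volume to protect the preterm lung and brain), in the deferred-consent rationale and in Choice of comparators.

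**The concern.** Infants of 23 to 28 weeks can die before 36 weeks corrected age. Death is the first secondary outcome, both pre-defined serious adverse events are deaths, and mortality is what the DSMB reviews at the interim. An infant who dies early cannot develop BPD at 36 weeks and accrues few days of support, oxygen or stay. If such an infant is entered at face value, an unfavourable course is scored as a favourable one.

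The first secondary research question asks whether volume targeting reduces BPD among other morbidities, and Sample size says "This study will be an initial trial for a large multi-center trial". Respiratory estimates that improve when mortality worsens would be a poor basis for that next step. The rationale leans on death or BPD, yet the trial does not plan to report it.

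**Working it through.** The Protocol gives no mortality, BPD or duration figures, so there is no stated figure to reproduce. From the Protocol: 25 infants per arm, two-sided 0.05. Everything else is assumed: mortality m of 10% in one arm and 20% in the other (2.5 and 5 expected deaths of 25), BPD b of 50% among survivors in both arms, and identical durations among survivors.

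**1. BPD**

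- Deaths counted as no BPD: (1 − m)·b. Lower-mortality arm 0.90 × 0.50 = 45%; higher-mortality arm 0.80 × 0.50 = 40%. The higher-mortality arm looks better.
- Survivors only: 50% in both. The reversal goes, but survivors are a post-randomisation subset and the comparison is no longer protected by randomisation.
- Death or BPD: m + (1 − m)·b. 0.10 + 0.45 = 55%; 0.20 + 0.40 = 60%. The higher-mortality arm is shown as worse.

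Range, same mortality (higher-mortality arm first):

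| BPD in survivors | BPD, deaths as no BPD | Death or BPD |
|---|---|---|
| 40% | 32% v 36% | 52% v 46% |
| 50% | 40% v 45% | 60% v 55% |
| 60% | 48% v 54% | 68% v 64% |

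At 24% against 8% mortality and b = 50%: 38% v 46%, and 62% v 54%.

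**2. Length of stay in raw days**

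The expected difference (higher- minus lower-mortality arm) is −(m₂ − m₁)·(S − D), with S the survivor mean and D the mean day of death.

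- S = 90, D = 14: −0.10 × 76 = −7.6 days. A simulation (survivors normal with SD 20, deaths uniform over days 0–28, 20,000 trials) gave −7.7 days, with t-test rejection in 12.8%.
- S = 85, D = 7: −0.10 × 78 = −7.8 days.
- S = 85, D = 40: −0.10 × 45 = −4.5 days.
- 24% v 8%, S = 90, D = 14: −0.16 × 76 = −12.2 days. Simulated −12.2, rejection 23.9%.

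Days alive and out of hospital to day 120 (horizon for illustration; 120 − 85 = 35 days per survivor, 0 for a death): 0.80 × 35 = 28.0 v 0.90 × 35 = 31.5, a difference of −3.5. Here fewer days is worse, so the direction is right.

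**3. The other durations, 20% v 10%, same formula**

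- Respiratory support (S = 55, D = 7): −0.10 × 48 = −4.8 days.
- Oxygen (S = 40, D = 7): −0.10 × 33 = −3.3 days.
- Ventilation (S = 10): −1.0 day if the infants who die have no ventilated days; +0.4 day if they have 14. The sign depends on the timing of death.

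**4. Equal true mortality**

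With m₁ = m₂ the formula gives 0. Simulation at 15% in both arms gave a mean difference of −0.1 day and rejection in 4.8%, so the test keeps its nominal level.

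**The case against.** The strongest reply is that how a death enters BPD or a duration is ordinary SAP content, and the SAP is not shown. That stands. A reader might infer that the Protocol prescribes raw days, with an early death scored as a short course. It does not: it names outcomes and tests only. A survivors-only summary fits the same words, and the Mann-Whitney test it names could rank death worst. What a handling rule would not supply by itself is an outcome that combines death with the respiratory course, because the outcome list is in the Protocol.

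A reader might also infer that chance imbalance in deaths makes the planned comparisons invalid. With equal true mortality, deaths would differ by 2 or more in 47% of trials of this size at 10% mortality and in 59% at 20%. That is sampling noise: it causes no bias on average and no inflation of error, and it moves the composite as well. Extreme splits are uncommon; exactly 5 v 1 in either direction has probability 2.6% at 10% mortality and 0.9% at 20%. At 3 v 1 with 50% BPD in survivors, the reversal is one infant each way (11 v 12 of 25 for BPD, 14 v 13 for the composite; chi-square p = 0.78 for BPD). Chance imbalance matters only when one realised trial with unequal deaths is read at face value.

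It is also fair to say that reporting components separately is legitimate, that mortality will be visible beside BPD and stay, and that citing a composite in the background does not oblige a feasibility trial to adopt it. These points lower the weight of the concern. They do not remove the advantage of an outcome whose direction stays interpretable when mortality differs.

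**Conclusion.** The point holds as a minor one. The Protocol names outcomes that death can pre-empt or shorten, compares outcomes with plain two-group tests, and lists nothing that combines them with death. If raw days are used, or deaths count as no BPD, an arm with truly higher mortality looks better: about 8 days shorter stay, and BPD of 40% v 45% where death or BPD is 60% v 55%. Those sizes rest on assumed mortality of 20% v 10%, 50% BPD in survivors, identical survivors and mostly early deaths; later deaths shrink the shift in stay.

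The text does not support calling this an error in a stated figure or a threat to the trial's main conclusion. There is no bias at equal true mortality, deaths are reported as their own outcome and reviewed by the DSMB, and the feasibility primary outcome is unaffected. The distortion lies more in the estimates than in the p-values, since the tests seldom reject at 25 per arm.

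**What to change.** By a dated amendment before unblinding:

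- Add death or BPD at 36 weeks as a secondary outcome.
- Report BPD among infants alive at 36 and at 40 weeks, with denominators shown.
- Report ventilation, respiratory support and oxygen as days alive and free of each, and stay as days alive and out of hospital, to a horizon fixed in advance; or rank death worst.
- Put survivor summaries beside mortality, and give between-arm differences with 95% confidence intervals, which suits the descriptive aim already stated.

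No new data are needed, since mortality, BPD and the durations are already collected. Recruitment began in October 2024, so the change is made mid-trial; under Who will be blinded, outcome assessors stay blinded until data lock, which leaves room to make it cleanly. Downsides: the composite gives death and BPD equal weight, and days-free measures depend on the chosen horizon.
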